4.3.1 Disenrollment

A study participant may elect to discontinue participation in the study at any time without disruption of their clinical care. If during follow-up, any laboratory testing indicates the presence of an infection, participants will be referred to clinical providers for further evaluation. If pregnant or if the protocol chair thinks it is in the woman's best interest, she will no longer be followed by the study. The study may be discontinued at any time by a participating IRB, the Office for Human Research Protections, or other government agency as part of their duties to ensure that research subjects are protected.

4.3.2 Participant referral

If a participant is diagnosed with any clinical issues during the course of study participation, they will be referred to a clinician or the health department to receive further testing and/or clinical care. Specifically, this refers to anyone diagnosed with any infection, pregnancy, or contraceptive issue. Clinical followup within 1 week will be encouraged for all participants and a written record relating to the clinical issue (test results, clinical finding or impression) will be provided to the participant.. Should they have a specific provider, it will be recommended that they contact that provider for an appointment. If the individual does not have a provider, we will facilitate getting the participant into care at the Grady Title X clinic or their health department for evaluation and/or treatment. We will follow-up with the participant within one week to confirm that they have sought appropriate care and if care has not been received, we will reinforce with the participant the importance of seeking treatment and actively assist in getting the participant into care.

5 Data and Biological Specimen Collection

Participants enrolled will undergo an interview, blood draw, and gynecologic exam with specimen collection at four study visits spanning 14 weeks.

5.1 Clinical evaluation

The clinical evaluation and all specimen collections will be performed by a study clinician or the trained study nurse using standard operating procedures determined prior to study initiation. All exam results will be documented on the biologic study clinical exam form (Appendix C). At the first visit, a urine HCG pregnancy test will be performed to document study eligibility after the consent form has been signed. Additionally a point-of-care HIV test will be administered to confirm

HIV negative status at baseline. At all visits, a pelvic exam will be performed. The clinician will examine for genital lesions and purulent vaginal discharge, and any abnormalities in the cervicovaginal mucosa will be documented on the physical exam data collection form. Wet-prep evaluations will be performed for bacterial vaginosis, yeast, and trichomoniasis during each pelvic exam. If during the course of study participation, any laboratory testing indicates the presence of infection, or if the participant's symptoms or physical examination raise suspicion of any other genital infection, a study clinician will refer for further care. There will be no extra information related to treatment or treatment outcomes recorded for study participants beyond what is standard of care. If during follow-up a woman is determined to be pregnant, she will be referred for care and no longer followed.

During the pelvic exam, vaginal pH will be measured with a pH meter, a vaginal swab will be collected for evaluation of vaginal microbiome, a swab for a multiplex PCR, a swab will be collected for a wet Prep, cervicovaginal fluid (CVF) will be collected by cervicovaginal lavage (CVL) for inflammatory marker quantification and two endocervical cytobrush samples of genital specimens for immune phenotyping. A swab will be collected into the anal opening to evaluate the gut microbiome. To enhance cellular yield from the posterior fornix of the FGT, CVL will be performed using 10 cc of phosphate buffered saline (PBS). Lavage will be repeated with a second aliquot of 10 cc of PBS. . Previous experience with this approach yielded $0.2-1 \times 10^6$ leukocytes per 10 cc of CVL, an amount of cells adequate for the proposed study endpoints and importantly avoided the need for the more invasive cervical cytobrush or vaginal biopsy sampling that also risks blood contamination of the sample. A second 10 cc of PBS will be collected in a similar

fashion to increase the potential yield for analysis. Obtained PBMC and CVL leukocytes will be processed and analyzed in real time for flow cytometry based phenotypic analysis. Additional CVL, vaginal swab, anal swab and plasma samples will be aliquoted and cryopreserved or frozen at -80°C until analyzed for other endpoints. [name] or a trained study nurse will perform all exams and sampling. Also at visit 2 and visit 4, a cervical or vaginal biopsy will be performed for a subset of participants that consent (10 per contraceptive arm) so that one or more samples of tissue from the vulva or vagina are acquired for evaluating HIV susceptibility and inflammation markers in the future.

In addition to the pelvic evaluation, blood will be collected at each visit in two 8 mL-vacutainer tubes (2 Cell Preparation Tubes (CPT)) for immunologic markers, and hormonal assessment (E2/P4 levels) at all four visits. Additional blood (1 Plasma Preparation Tube (PPT) will be collected at visit one for syphilis with rapid plasma reagin (RPR), HIV and HSV serology at the research lab. Table 4 lists the schedule of events and biologic specimen collection for the study. The collection of specimens at each visit will be noted on the specimen collection form (Appendix D). Positive test results from the research lab can not be relied upon for patient care. Any positive test results concerning for infection from the research lab will trigger further clinical investigation with referral for further testing and treatment.

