4.1.3 Eligibility

Participants who meet all of the following ***inclusion criteria*** will be eligible for the study (a) female (b) age 18-45 years, (c) normal menses (22-35 day intervals) for at least 3 cycles, (d) intact uterus and cervix, (e) interested in DMPA, Nexplanon, Mirena IUD, or Copper IUD (f) willing to delay initiation of hormonal contraception for up to 1 month to complete pre-contraceptive study visits, (g) willing to use condoms or abstain from sexual intercourse for at least 24 hours before each genital tract sampling (condoms will be made available), (h) able and willing to provide informed consent, and undergo serial blood and vaginal sampling, (i) negative HIV screening.

Participants who meet any of the following ***exclusion criteria*** will not be eligible for the study: (a) pregnant within the last 3 months (b) breastfeeding, (c) history of loop electrosurgical excision procedure, conization, or cryosurgery within the past year, (d) use of hormonal contraception or IUD in the past 6 months or, (e) known history of medical condition that would interfere with the conduct of the study, (f) symptomatic vaginal infection or genital ulcer disease at screening, (g) taking medications that interact with selected contraceptive, and (h) contraindications to selected contraceptive per the CDC medical eligibility criteria(67) or judgment of clinician. For the copper IUD, exclusion criteria: allergy to copper. Participants who agree to the cervical and vaginal biopsy will have the addition exclusion criteria: allergy to lidocaine.

The cost of their selected contraceptive will be covered by research study funds. They will be informed of this during the consenting process.

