Data Management and Statistical Analysis: Study data will be recorded on case report forms and entered into a web-based password-protected relational database (REDCap). Repeated-measures analyses using mixed linear models will be performed with the assistance of Emory CFAR biostatistical core for study endpoints and analyzed with SAS Proc Mixed (version 9) providing separate estimates of the means by contraceptive method and time on study before (weeks 1 and 3) and after (15 and 17 weeks) contraceptive administration. An unstructured variance-covariance form among the repeated measurements will be assumed for each outcome and estimates of the standard errors of parameters will be used to perform statistical tests and construct 95% confidence intervals. The model-based means are unbiased with unbalanced and missing data,

assuming missing data are non-informative and random. Mean changes over time for each contraceptive method will be tested for linear trend. Data will be summarized using adjusted means and observed differences plus 95% confidence intervals. Statistical tests will be 2-sided. A P value ≤ 0.05 will be considered statistically significant.

For multivariable repeated-measures analyses, a mixed linear model will be fit including age, body mass index, race and parity as potential baseline confounders in addition to contraceptive method, time on study and the interaction between time on study and contraceptive method. The multivariable results will be summarized with adjusted means and 95% confidence intervals. The adjusted mean for each contraceptive subgroup (DMPA, Nexplanon, copper IUD and Mirena IUD) will be defined as the mean response obtained by fitting the statistical model at the mean age and the mean BMI of the three subgroups and averaged across levels of the other risk factors. To integrate time-dependent variables, such as BV and PSA, into the longitudinal analyses, each participant at each of the 4 scheduled visits will be classified as positive or negative for each variable. Outcome change will be compared between incident cases and the other women (baseline positive and those that remain negative) after adjusting for the other covariates.

9 Dissemination of Results

The results will be disseminated in the form of abstracts submitted to scientific meetings and manuscripts submitted to peer-reviewed journals.

REFERENCES

1. UNAIDS. UNAIDS Report on the global AIDS epidemic. 2010.

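### Baseline infections are detected and referred for treatment before the post-contraceptive samples, but treatment is not planned as study data and no planned analysis separates clearance from the contraceptive effect

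*Combined protocol and SAP*

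**What the plan says.** **Entry.** The only infection-related exclusion in section 4.1.3, apart from HIV, is "symptomatic vaginal infection or genital ulcer disease at screening". Asymptomatic bacterial vaginosis, yeast or a sexually transmitted infection (STI) does not exclude. In the section 4.1.6 visit table, the swabs for STI PCR, wet prep and Nugent score are scheduled at visits 1 to 4 and not at screening.

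**Action on a positive result.** Section 5.1: "Any positive test results concerning for infection from the research lab will trigger further clinical investigation with referral for further testing and treatment". Section 4.3.2 adds "We will follow-up with the participant within one week to confirm that they have sought appropriate care", with active help into care if none has been received.

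**Recording.** Section 5.1: "There will be no extra information related to treatment or treatment outcomes recorded for study participants beyond what is standard of care". The visit questionnaire in section 4.2 covers sexual behaviour and bleeding or vaginal symptoms. The interval assessment in section 4.1.6 covers menstruation and contraceptive use. Neither mentions anti-infective treatment.

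**Analysis.** Section 8 estimates means by method "before (weeks 1 and 3) and after (15 and 17 weeks) contraceptive administration". The multivariable model adds method, time and their interaction to a covariate set "including age, body mass index, race and parity as potential baseline confounders". For time-dependent variables, with BV and PSA as the examples, "each participant at each of the 4 scheduled visits will be classified as positive or negative for each variable". The outcome change is then compared between incident cases and everyone else, and that second group expressly combines baseline positives with women who stay negative. Table 5 in section 5.2 lists the STI screen, Candida and BV as covariates for all aims, but section 8 does not say how they enter the method contrast.

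**The concern.** Section 2.1 names STIs among the factors that change local immune status and the population of HIV target cells, and it links normal flora free of BV to natural resistance. These immune quantities are the outcomes of Aims 1 to 3. The study's own testing can lead to treatment of baseline infections after the visit 1 or 2 sample and before weeks 15 and 17. Part of the pre/post change may then reflect clearance of infection and not the contraceptive.

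For the hypothesised increases in target cells, activation and proinflammatory markers, a fall on clearance works against the hypothesis. It can hide an increase, or make a method with no effect look as if it lowers inflammation. The contrasts of DMPA with Nexplanon and with the Mirena IUD are affected only if baseline infection or its clearance differs by arm. Women choose their own method (section 4.1.1), so equality is not assured.

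**Working it through.** **1. The plan's own figures.** Section 8 uses an SD of change of 17.4 points for CCR5 and 11 for CD38, with two-sided alpha of 0.05. Noncentral-t power:

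- One sample, n = 90, change of 10: 99.97% for CCR5 and above 99.99% for CD38 (stated: exceeding 95%).
- Two samples, 30 per group: 90.7% for a 15-point CCR5 difference (stated 90%) and 93.3% for a 10-point CD38 difference (stated 93%).

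The stated powers reproduce and are not in dispute.

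**2. Inputs the documents do not give.** Let p be the share of women with an infection at visit 1 or 2 that clears before week 15, and d the fall in the marker on clearance. Assumed here: p = 10% to 40%, d = 10 points.

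**3. Pre/post shift.** If the infection is present at both pre-contraceptive visits, the mean change moves by −p × d. If it is present at visit 1, clears before visit 2, and the two visits are averaged as the baseline, half of the fall is already in the baseline and the shift is −p × d / 2.

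| p | p × d | p × d / 2 |
|---|---|---|
| 10% | 0.10 × 10 = 1 | 0.5 |
| 20% | 0.20 × 10 = 2 | 1 |
| 40% | 0.40 × 10 = 4 | 2 |

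Against the planned 10-point increase, the range is 0.5 to 4 points, or 5% to 40%. The shift is proportional to d, so d = 5 halves every entry.

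**4. Consequence for the pre/post tests.** The mixture of cleared and other women raises the SD to √(SD² + p(1 − p)d²).

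- True increase of 10, n = 90, p = 40%, full shift: the expected change is 6 and the CCR5 SD is √(17.4² + 0.24 × 100) = 18.1. Power is 87.6% for CCR5 and 99.7% for CD38.
- No true effect, one arm of 30, p = 20%, full shift of 2: the chance of a significant result, mostly an apparent decrease, is 9.1% for CCR5 and 14.8% for CD38, against a nominal 5%.

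**5. Between methods.** Bias = (difference in p) × d, halved in the same way if visit 1 infections clear before visit 2. With equal p and d in both arms it is zero. With a 20-point difference, 0.20 × 10 = 2 points, or 1 point when halved. Against the planned 15-point CCR5 difference, that is 2/15 = 13% or 1/15 = 7%.

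| Bias | CCR5 power (unbiased 90.7%) | CD38 power (unbiased 93.3%) |
|---|---|---|
| 1 point | 86.5% or 93.8% | 87.6% or 96.8% |
| 2 points | 81.2% or 96.1% | 79.1% or 98.6% |

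The two values in each cell are for bias against and in favour of the planned difference.

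**6. What the planned data can show.** A woman positive at visit 1 or 2 and negative at visits 3 and 4 is identifiable from the scheduled tests. Under the stated comparison in section 8 she is nevertheless in the reference group with women who were never positive. The tests do not show whether she was treated, with what, or when.

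**The case against.** The strongest case on the other side has five parts.

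- **Infection is measured and partly planned for.** It is tested at all four visits, Table 5 lists it as a covariate, and section 6.5 concedes confounding and promises covariate control. A reader might infer from section 5.1 that the problem could never be examined afterwards. The documents do not support that: clearance is visible, and excluding women positive at visit 1 or 2 needs no treatment data. What stands is that no planned analysis isolates these women.
- **The recording sentence is qualified.** It rules out only extra information beyond standard of care, so clinical records may hold the treatment, and the examination form in Appendix C is not available to check. A reader might infer that treatment goes wholly unrecorded, which the text does not say. Still, section 4.3.2 sends women to their own provider, the Title X clinic or the health department, and no retrieval of those records is described.
- **Treatment before week 15 is not certain.** Research results lead first to clinical investigation, no PCR turnaround is given, and uptake is unknown. This stands, and is why p is only an assumption.
- **The size is assumed.** A 10-point fall is 10/17.6 = 57% of the mean CCR5 used for planning. A 2-point bias between arms is 2/17.4 = 0.11 SD, and nothing in the documents points to a 20-point prevalence gap. This stands.
- **Removing every woman treated during follow-up would introduce its own bias.** Section 2.1 associates progestin contraceptives with candidiasis and STIs and progesterone with a predisposition to BV, leaving open whether the cause is biological or behavioural. Infection arising after initiation may be a consequence of the method. This stands and shapes the fix.

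**Conclusion.** The concern holds in a limited form. Asymptomatic infection is admitted, found and referred for care before the post-contraceptive samples. Treatment is not planned as study data, and the stated use of infection status combines baseline positives with never-positives. Clearance can therefore lower post-contraceptive markers. It biases the between-method contrast only if baseline infection or its clearance differs by chosen method.

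The size cannot be determined from the documents. Under the assumed p of 10% to 40% and d of 10 points, it is about 0.5 to 4 points pre/post against a planned 10. With a 20-point prevalence gap it is about 1 to 2 points between methods against a planned 15.

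The documents do not support a claim that the results will be biased by a known amount, or that the method comparison is invalid. In a study that describes itself as exploratory, this is a cheap improvement and not a defect that stops the study.

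**What to change.** None of these changes alters referral or clinical care.

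1. **Section 5.1.** Replace the sentence on treatment information with one stating that any anti-infective treatment (yes/no, drug class, date) will be recorded at the existing one-week contact and at each visit's interval assessment.
2. **Section 8, sensitivity analysis.** Report the pre/post and between-method contrasts in all women, and again excluding women with an infection detected at visit 1 or 2. Both samples are scheduled as pre-contraceptive, so this exclusion does not condition on an effect of the method.
3. **Section 8, incident-case comparison.** Separate baseline-positive women, split into cleared and persistent, from women who remain negative. Treat the cleared/persistent split as descriptive, since later status may depend on the method.
4. **After initiation.** Do not exclude women for infection or treatment arising after contraceptive start. Describe them separately by arm.

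The cost is one case report form item at contacts that already take place, one extra analysis, and a less precise sensitivity set. With p of 10% to 40%, 3 to 12 of 30 women per arm would be removed, leaving 18 to 27. At an unchanged SD, confidence intervals widen by a factor of about √(30/27) = 1.05 to √(30/18) = 1.29.

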5.2 Laboratory testing

All laboratory results from assays on blood or vaginal swabs, and CVL will be documented on the laboratory results forms (Appendix E).

Specimens collected will be transported within 4 hours to the lab. Blood will be separated and immediately processed for immunophenotyping and immune cell-activation assays, as described below for the vaginal samples. The separated plasma will be aliquoted and stored at -80°C until batch testing commences, as described below for the vaginal samples. Progesterone (P4) and estrogen (E2) levels will be measured in plasma using the Milliplex kit for Luminex Assay (EMD Millipore, Billerica, MA).

A vaginal swab and anal swab will be collected and stored for future microbiome characterization via next-generation sequencing using the Ion Torrent platform to sequence 16S rDNA from bacterial species present in the vaginal compartment.

The CVL specimens will be tested for blood and leukocyte levels with a urine dipstick test and prostate specific antigen (PSA), a marker of semen exposure, using the Abacus ABACard p30 test. The sample will be centrifuged, and the cell pellet will be re-suspended in cell culture media,

Table 5: Summary of Covariates and Analytic Methods for All Specific Aims

Demographics/Behaviors: Questionnaire/Exam: Age, BMI, Race, Parity, Coital frequency

STD Screen: Vaginal swab multiplex PCR for *N.gonorrhoea*, *C. trachomatis*, *T. vaginalis*, *M. genitalium*, *T. pallidum*, HSV-1 & 2. Serum EIA for HIV & HSV. Serum RPR Kit for RPR

Candida vaginitis: Vaginal swab for KOH wet mount examination for hyphae (yeast)

Bacterial Vaginosis: Vaginal swab for gram stain assessment for Nugent score BV diagnosis

Semen: CVL supernatant ABACard® testing for qualitative prostatic specific antigen (PSA)

Serum sex hormones: Serum RIA for E2, P4

Microbiome: Next generation sequencing of 16s rDNA

and the leukocytes will be isolated from epithelial cells using Percoll gradient centrifugation. The resuspended CVL cell pellet (and PBMC pellet, separately) will be split for analysis. One half of the sample will be used for immune cell characterization (i.e., T cell subsets, HIV co-receptor expression) by antibody staining and multi-color flow cytometry using a LSR-2 platform. The other

half of the sample will be used to assess functional attributes of the T-cells. Cells will be stimulated with PMA and ionomycin (a polyclonal activator) in a tissue culture dish for 5 hours in the presence of brefeldin A and monensin and analyzed for the production of selected cytokines and chemokines by flow cytometry. *Multicolor flow cytometry* will be performed on matched PBMC and CVL samples utilizing the LSR-II platform (BD Biosciences) as previously described.(68) For assessment of HIV target cells, samples will be stained with a Live/Dead viability dye and fluorochrome labeled antibodies against CD3, CD4, CD27, CD45RA, CCR5 and CXCR4. Effector memory (CD45RA-/CD27-) CD3+CD4+ cells will be analyzed for surface expression of HIV co-receptors CCR5 and CXCR4 and reported as percent of total leukocytes and total CD4+ T cells.

We will examine a panel of proinflammatory, anti-inflammatory, inhibitory and chemotactic cytokines and chemokines, focusing our analysis on those previously reported to influence recruitment of HIV target cells to the FRT such as IL1 and IP10(69). Using multiplex Luminex® assays combined with a customized multi-analytical panel of 22 human cytokines and chemokines, we will quantify concentrations of cytokines and chemokines in plasma and CVL supernatant at each study visit from participants enrolled

Recent semen exposure will be measured with a qualitative PSA ABACard® p30 test (Abacus Diagnostics) (70). The wet-mount will be evaluated using saline and 10% KOH for evaluation of budding yeast or hyphae. A gram stain will be performed for Nugent scoring (71) to diagnose BV. A multiplex PCR assay, able to screen for multiple STIs concurrently without the need for multiple samples to be collected, will be used to evaluate for STIs including *N. gonorrhoea*, *C. trachomatis*, *T. vaginalis*, *M. genitalium*, *T. pallidum*, and HSV-1/HSV-2. Serological tests for HIV

and HSV will be performed via enzyme immunoassay (EIA) using a Vitros® 3600 Immunodiagnostic system (Ortho Clinical Diagnostics) and syphilis screening determined via a commercially available rapid plasma reagin (RPR) kit. Positive test results from the research lab can not be relied upon for patient care. Any positive test results concerning for infection from the research lab will trigger further clinical investigation with referral for further testing performed by a CLIA-approved laboratory and treatment.

Table 6. Biological specimens and laboratory methods

Sample	Analytic Method	Outcomes of Interest
Cells from CVL and PBMC	Multi-parameter flow cytometry	
 • T cell subtypes: CD4, CD8, CCR7, CD25, CD27, CD28, CD45RA+, CD57, CD11a, PD1, HLA-DR. • HIV co-receptor use: CCR5, CXCR6, CXCR4. • T cell functional attributes: IFNγ, TNFα, IL-2, MIP1α, MIP1β.
CVL Supernatant	Luminex panel	
 • Proinflammatory: IL-1β, IL-6, IL-12 (p70), G-CSF, M-CSF, IFN-α2, IFN-γ, IL-1α, IL-17, IL-2, TNF-α, TNF-β, IL-4, IL-5 • Anti-inflammatory: IL-10 • Inhibitory (CCR5 agonists): RANTES, MIP-1α, MIP-1β • Chemotaxic: IP10, IL-8, MCP-1, Eotaxin • PSA
Plasma	ABBA Card RIA RPR Kit EIA	
 • Plasma progesterone concentrations. • RPR • HIV/HSV
Vaginal, endocervical and Anal Swabs	Next-generation sequencing using	
 • 16S rDNA from bacterial species present in the vaginal compartment

	
the Ion Torrent platform
 
Mulitplex PCR
 
 • N.gonorrhea, C. trachomatis, T. vaginalis, M. genitalium, T. pallidum, HSV-1 & 2.
--	--

